#### 16.2 Interviews, questionnaires, and/or surveys will be administered or focus groups will be conducted:

Yes  No

List any standard instruments used for this study:

- Clinical Dementia Rating Scale (Morris, 1993)
- Montreal Cognitive Assessment (MoCA) (Nasreddine, 2005)
- Disability Assessment for Dementia (DAD) (Gelinas and Gauthier, 1994)
- Alzheimer's Disease Assessment Scale – Cognitive Subscale (ADAS-cog) (Rosen 1984)
- Physical Performance Battery (SPPB) (Guralnick 1994)
- Senior Fitness Test (SFT) (Rikli & Jones 2002)
- Neuropsychiatric Inventory (NPI) (Cummings 1997)
- Falls Efficacy Scale (FES) (Hauer 2010)
- Quality of Life Scale in Alzheimer's Disease (QOL-AD) (Logsdon 1999)
- Geriatric Depression Scale (GDS) (Sheikh and Yesavage, 1986)
- Caregiver Burden Inventory (CBI) (Novak 1989)
- Positive Aspects of Caregiving (PAC) (Tarlow 2004)
- Verbal Fluency Task (Lezak 1995)
- SF-36 (Ware 1992)

Attach any non-standard instruments at the end of the application.

#### 16.3 Conduct of study procedures or tests off-site by non-UCSF personnel:

Yes  No

If yes, explain:

#### 16.4 Sharing of experimental research test results with subjects or their care providers:

Yes  No

If yes, explain:

Findings from the study may be shared with study participants or caregivers in aggregate form. Individual data will not be shared. Results may be shared by letter, email, in person or other means based on affected individual, caregiver or investigator preferences.

#### 16.5 \* Specimen collection for future research and/or specimen repository/bank administration:

Yes  No

#### 16.6 Time commitment (per visit and in total):

##### Affected Individual

- Consent/eligibility visit (1 hour)
- Baseline assessment (1 - 1.5 hours)
- Intervention (1 hour, 2 days/week for 12 weeks: 24 classes total)
- Home visits (1 hour, 3 visits total)

- Total: 33 hours over 12 months
- Home practice: additional 1-2 hours/week

#### Caregiver

- Consent/eligibility visit (1 hour)
- Baseline assessment (1 hour)
- Intervention (1 hour, 2 days/week for 12 weeks: 24 hours total)
- Home visits (3 visits, 1 hour each: 3 hours total)
- Monthly telephone check-ins (9 calls, 20 minutes each: 3 hours total)
- Post-intervention assessments (3, 6 and 9 months, 1 hour each: 3 hours total)
- Total: 36 hours over 12 months
- Home practice: additional 1-2 hours/week

#### Qualitative Interview Substudy:

- 2 interviews 1 hour each
- Questionnaire and daily log: 1-2 hours over 1 month
- Home practice: additional 1-2 hours/week for 1 month

### **16.7 Locations:**

All study procedures will take place at Kaiser Permanente in Oakland and at ASEB in Berkeley, CA. Visits with caregivers may occur at an alternate location (e.g., home) if requested. Interviews for the qualitative substudy will be conducted in the participants' homes.

### **16.8 Describe the resources in place to conduct this study in a way that assures protection of the rights and welfare of participants:**

The safety and welfare of study participants who are affected individuals will be ensured by performing all exercise-related study procedures and assessments with their caregivers together. Study personnel who assess for eligibility, obtain consent and administer study questionnaires are already extensively trained in how to work with individuals with mild-to-moderate dementia and caregivers in a sensitive and respectful manner. Class size will be limited to 5 dyads and 2 or more instructors to ensure the safety of study participants. Exercise instructors are certified in at least one type of exercise training and are extensively trained in how to safely work with individuals with mild-to-moderate dementia. Data and recordings will be maintained on secure servers or in locked file cabinets.

## **17.0 Risks and Benefits**

### **17.1 \* Risks and discomforts:**

As with any program involving new exercises, study participants may experience injuries including muscle strain or soreness, joint pain, falls or other injuries. In addition, study participants may find the baseline or follow-up assessments or video-recording to be stressful. Loss to privacy may occur if information is released outside the study team.

### **17.2 Steps taken to minimize risks to subjects:**

For our prior PLIE study, we have consulted with a wide range of experts who have experience leading exercise classes for individuals with mild-to-moderate dementia to ensure that the exercise program is safe and likely to be effective. These included local, national and international experts in traditional exercise programs as well as Tai Chi, Feldenkrais, and yoga. We will minimize stress during baseline and post-intervention assessments by having trained research staff to recognize and appropriately address signs of discomfort or stress when indicated (e.g., taking breaks, rescheduling appointment, skipping sections that cause undue discomfort). We will minimize risk of loss of privacy by having trained all research staff to maintain data in a secure manner and not to discuss study participants outside the research team. When it is necessary to carry private information offsite (e.g., names on class attendance logs, addresses for home visits), information will be carried in a locking device such as a briefcase. If caregivers request to communicate by mail, email, fax or text, they will be informed that this may increase the risk of loss of privacy. These communications will include a confidentiality statement, and the minimum

amount of identifying information necessary will be conveyed. Study forms will include unique ID numbers but not names or other identifying information. All research staff involved in this study have already been part of the PLIE study and are well trained. Recordings will be stored on a secured data server (MyResearch) and/or on an encrypted external hard drive stored in a secure locked file cabinet. Separate consent will be obtained for public release of video recordings and future contact.

Audio-recorded interviews for the substudy will be uploaded to MyResearch and subsequently deleted from the recorder.

### **17.3 Benefits to subjects:**

Yes  No

If yes, describe:

Some affected individuals may experience improvements in physical, emotional or cognitive function, but this is not guaranteed. Caregivers may experience a reduction in caregiver burden or improved well-being, but this is not guaranteed.

### **17.4 Benefits to society:**

This study will determine the impact of the Paired PLIE Program on function and well-being in individuals with mild-to-moderate cognitive impairment and their care partners. If this program is successful, it could substantially improve quality of life for individuals with dementia and their caregivers.

### **17.5 Explain why the risks to subjects are reasonable:**

The risks to subjects are comparable to daily life experiences related to engaging in physical activity or in being assessed in a clinical setting.

## **18.0 Confidentiality and Privacy**

### **18.1 Plans for maintaining privacy in the research setting:**

Data will be entered into the MyResearch portal, which provides a secure web-based data management and storage system for UCSF investigators, and will not be stored electronically on computers or servers. Paper copies of data collection forms and video footage will be stored in locked files cabinets. Subjects will be identified by a unique participant identification number. Personal identifying information will be stored separately and securely. Video-recording will include identifiable faces and first names and will be stored electronically on the same secured server or an encrypted external hard drive stored in a secured locked file cabinet. No last names will be used and video-recordings will not be published or visible to anybody outside the research team or scientific meetings without additional written consent from study participants. At the caregiver participant's request, communication may be conducted via mail, email, fax or text. Caregivers will be informed that these modes of communication may increase their risk of loss of privacy. Mail, email, fax and text communications will include a confidentiality statement. The minimum amount of identifying information will be included in all communications. Study forms will include unique study ID numbers only.

### **18.2 Possible consequences to subjects resulting from a loss of privacy:**

Loss of privacy could potentially result in stigma related to dementia diagnoses or test scores.

### **18.3 Study data are:**

Derived from the Integrated Data Repository (IDR) or The Health Record Data Service (THREDS) at SFGH

Derived from a survey (check all that apply) (e.g., N=5, Open-End, Likert, etc.)

- Added to the hospital or clinical medical record
- Created or collected as part of health care
- Used to make health care decisions
- Obtained from the subject, including interviews, questionnaires
- Obtained from a foreign country or countries only
- Obtained from records open to the public
- Obtained from existing research records
- None of the above

If **derived from a medical record**, identify source:

---

#### 18.4 Identifiers may be included in research records:

Yes  No

If **yes**, check all the identifiers that may be included:

- Names
- Dates
- Postal addresses
- Phone numbers
- Fax numbers
- Email addresses
- Social Security Numbers\*
- Medical record numbers
- Health plan numbers
- Account numbers
- License or certificate numbers
- Vehicle ID numbers
- Device identifiers or serial numbers
- Web URLs
- IP address numbers
- Biometric identifiers
- Facial photos or other identifiable images
- Any other unique identifier

\* Required for studies conducted at the VAMC

#### 18.5 Identifiable information might be disclosed as part of study activities:

Yes  No

If **yes**, indicate to whom identifiable information may be disclosed:

- The subject's medical record
- The study sponsor
- Collaborators
- The US Food & Drug Administration (FDA)
- Others (specify below)
- A Foreign Country or Countries (specify below)

If **Others**, specify:

Medical personnel if study-related injury. Auditors.

**18.6 Indicate how data are kept secure and protected from improper use and disclosure (check all that apply): NOTE: Whenever possible, do not store subject identifiers on laptops, PDAs, or other portable devices. If you collect subject identifiers on portable devices, you MUST encrypt the devices.**

- Data are stored securely in My Research
- Data are coded; data key is destroyed at end of study
- Data are coded; data key is kept separately and securely
- Data are kept in a locked file cabinet
- Data are kept in a locked office or suite
- Electronic data are protected with a password
- Data are stored on a secure network
- Data are collected/stored using REDCap or REDCap Survey
- Data are securely stored in OnCore

**18.7 Additional measures to assure confidentiality and protect identifiers from improper use and disclosure, if any:**

Research staff are HIPAA-trained and are instructed not to discuss or disclose information about study participants outside the research team.

**18.8 This study may collect information that State or Federal law requires to be reported to other officials or ethically requires action:**

- Yes
- No

Explain:

Interviews with subjects or caregivers could potentially reveal information related to abuse or thoughts of suicide or homicide.

**18.9 This study will be issued a Certificate of Confidentiality:**

- Yes
- No

## 19.0 Subjects

**19.1 Check all types of subjects that may be enrolled:**

- Inpatients
- Outpatients
- Healthy volunteers
- Staff of UCSF or affiliated institutions

**19.2 Additional vulnerable populations:**

- Children
- Subjects unable to consent for themselves
- Subjects unable to consent for themselves (emergency setting)
- Subjects with diminished capacity to consent
- Subjects unable to read, speak or understand English
- Pregnant women
- Fetuses
- Neonates

- Prisoners
- Economically or educationally disadvantaged persons
- Investigators' staff
- Students

Explain why it is appropriate to include the types of subjects checked above in this particular study:

The goal of the study is to determine whether the Paired PLIE program improves function and quality of life in individuals with mild-to-moderate cognitive impairment. Therefore, although study participants will have a diminished capacity to provide consent, findings from the study could potentially improve quality of life for some study participants and provide important data for others with mild-to-moderate cognitive impairment.

Describe the additional safeguards that have been included in the study to protect the rights and welfare of these subjects and minimize coercion or undue influence:

Informed consent will be obtained from both study participants--affected individuals and their caregivers/LARs--together if possible. Capacity to consent will be determined using a standard protocol that is based on the protocol used at the UCSF Memory and Aging Center. Subjects who are able to consent for themselves will do so. Subjects who do not demonstrate capacity to consent will be asked for assent and LARs will provide consent on their behalf.

## 20.0 Recruitment

### 20.1 \* Methods (check all that apply):

- Study investigators (and/or affiliated nurses or staff) recruit their own patients directly in person or by phone.
- Study investigators recruit their own patients by letter. Attach the letter for review.
- Study investigators send a "Dear Doctor" letter to colleagues asking for referrals of eligible patients. If interested, the patient will contact the PI or the PI may directly recruit the patients (with documented permission from the patient). Investigators may give the referring physicians a study information sheet for the patients.
- Study investigators provide their colleagues with a "Dear Patient" letter describing the study. This letter can be signed by the treating physicians and would inform the patients how to contact the study investigators. The study investigators may not have access to patient names and addresses for mailing
- Advertisements, notices, and/or media used to recruit subjects. Interested subjects initiate contact with study investigators. Attach ads, notices, or media text for review. In section below, please explain where ads will be posted.
- Study investigators identify prospective subjects through chart review. (Study investigators request a Waiver of Authorization for recruitment purposes.)
- Large-scale epidemiological studies and/or population-based studies: Prospective subjects are identified through a registry or medical records and contacted by someone other than their personal physician. (Study investigators request a Waiver of Authorization for recruitment purposes.)
- Direct contact of potential subjects who have previously given consent to be contacted for participation in research. Clinic or program develops a CHR-approved recruitment protocol that asks patients if they agree to be contacted for research (a recruitment database) or consent for future contact was documented using the consent form for another CHR-approved study.
- Study investigators list the study on the School of Medicine list of UCSF Clinical Trials website or a similarly managed site. Interested subjects initiate contact with investigators.
- Study investigators recruit potential subjects who are unknown to them through methods such as snowball sampling, direct approach, use of social networks, and random digit dialing.
- Other

If **Other**, explain:

Study participants will be recruited using a variety of methods including: distribution of study fliers at caregiver support groups meetings (e.g., Kaiser, ASFB, Alzheimer's Association); posting

fliers in community settings (e.g., senior centers); posting fliers online (e.g., Facebook); and distributing letters and fliers to clinicians and other community members. Individuals who express interest in learning more about the study will be contacted by telephone by research staff, who will describe the study procedures and obtain verbal consent to be screened. Those who are eligible and interested will be scheduled for an in-person consent visit.

Qualitative sub-study participants will be recruited from current study participants who have completed the intervention and have provided consent to be contacted about this research study. Potential participants will be contacted in the order in which they were originally enrolled until our target sample size is reached.

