## 11.0 Study Design

### 11.1 \* Study design (Help Text updated 9/13):

We propose to perform a randomized, controlled trial (RCT) with a delayed start design to examine the effects of the Paired PLIÉ program in individuals with cognitive impairment and their care partners over 9 months. Study participants will be 60 pairs of individuals with mild-to-moderate cognitive impairment and their primary care partners. Study pairs will be enrolled in blocks of 10 and will be randomly assigned to Group 1 (immediate start, n=5) or Group 2 (3-month delayed start, n=5). Pairs randomized to Group 1 will participate together in the Paired PLIÉ program 2 days/week for 12 weeks (24 classes total) while pairs randomized to Group 2 will continue with their usual activities. After 3 months, Group 1 will transition into a maintenance phase, and Group 2 will participate in the Paired PLIÉ program 2 days/week for 12 weeks. Outcome data will be collected in all study participants at baseline and 3, and 6 months. We have partnered with local community-based organizations that have agreed to serve as study sites and to assist with recruitment efforts.

We will conduct a sub-study with semi-structured interviews in a sub-sample of our participants. The goal is to assess motivations and barriers for home practice of the exercises taught in the intervention classes and to develop improved support materials (brochures, video clips on DVD and/or YouTube) according to feedback from participants.

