#### **12.2 \* List the specific aims:**

Aim 1. To determine whether Paired PLIÉ improves participant outcomes over 9 months.

Aim 2. To determine whether Paired PLIE improves caregiver outcomes over 9 months.

Sub-Study: To develop improved support material for home practice.

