**9. Post-intervention.** Study participants will be provided with an illustrated booklet and access to videos (e.g., DVD or YouTube) to support home-based practice. Findings from the study may be provided to subjects and caregivers in aggregate form (i.e., without identifying individual subjects). Study participants will sign separate consent for future contact.

**10. Qualitative Interview Substudy.** Study participants who have completed the intervention and have agreed to future contact related to this research study will be contacted by telephone and asked if they would be interested in participating in a substudy that would involve semi-structured interviews conducted in their homes. Two research team members (including at least one exercise instructor) will conduct the home visits and interviews. This sub-study will require participants to sign a separate consent form and to consent/assent specifically for this sub-study. The topic of the interview is to solicit answers to (1) questions about motivators and barriers to home exercise practice and (2) questions about participants' wishes for written and/or electronic material that may support home practice. We will initially recruit 5 dyads for a 1-hour interview. Semi-structured interviews will follow an interview guide, will be audio-recorded and transcribed. We will develop new support material following the suggestions of the interviewees. We are planning to improve the exercise brochure and create a series of new and shorter video clips for DVD or YouTube according to the feedback of the participants. This material will be given to these participants for a month of home application followed by a second interview and asking for a written evaluation. Participants will also answer a brief questionnaire about facilitators and barriers for home practice and use a log for daily entries about their exercises and study-related movements. The second interview may prompt iterative revision of our support material, which we will provide to a second group of 5 dyads undergoing the same two interviews. Following the completion of all interviews, the support material will undergo a final professional production which we plan to include in a larger multi-site study of our Paired PLIE Program.

Audio recordings will be stored and--after study completion--deleted the exact same way as the video-recordings.

If you have a procedure table, attach it to the submission with your other study documents.

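### The sub-study entry rule does not wait for the last outcome visit, so up to 10 dyads could receive extra home-practice support during follow-up, and before month 6 only in Group 1

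*Combined protocol and SAP*

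**What the plan says.** **Entry rule.** Section 20.1: "Qualitative sub-study participants will be recruited from current study participants who have completed the intervention". Section 16.1 item 10: "Study participants who have completed the intervention and have agreed to future contact related to this research study will be contacted by telephone". Neither mentions outcome visits.

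**Order and number.** Section 20.1: "Potential participants will be contacted in the order in which they were originally enrolled until our target sample size is reached". Section 16.1 item 10: "We will initially recruit 5 dyads for a 1-hour interview", followed by revised material "which we will provide to a second group of 5 dyads undergoing the same two interviews". Section 12.3, however, refers to 10 interviews.

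**What sub-study dyads receive.** Item 10 describes two home interviews by a two-person team that includes an exercise instructor, new brochures and shorter clips, a questionnaire and a daily exercise log. Of the material it says: "This material will be given to these participants for a month of home application followed by a second interview".

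**Timing in the main trial.** Section 11.1: "After 3 months, Group 1 will transition into a maintenance phase", while Group 2 then takes its 12 weeks of classes. Section 12.2: "Aim 1. To determine whether Paired PLIÉ improves participant outcomes over 9 months". Outcomes are at 0, 3, 6 and 9 months in sections 12.3 and 16.1 item 5, and the caregiver schedule in 16.6 also lists month 9. Section 11.1 stops at month 6.

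**The concern.** The sub-study is not passive. Section 13.1 says its purpose is to learn whether better material can make home exercise more motivating and feasible. Once classes stop, home practice is the main part of the programme that continues. A dyad that joins before its last visit would contribute later scores that reflect Paired PLIÉ plus support the other dyads do not get.

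The two arms become eligible three months apart, so the extra support could fall unevenly between them. What is at stake is the month-6 and month-9 results and the reading of Group 1's maintenance phase. These are the visits that distinguish the 9-month aims from a 3-month comparison.

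**Working it through.** **1. The plan's own figures.** Section 14.4 uses 1 pre and 3 post measures, correlation 0.75 and alpha 0.05 (two-sided assumed). Section 13.2 gives pilot effects of 0.49 to 0.83. For the mean of three post measures minus baseline, the variance factor is

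V = (1 + 2 × 0.75)/3 + 1 − 2 × 0.75 = 0.333.

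With n = 2(1.960 + 0.842)² × V / d²:
- d = 0.83: 5.23/0.689 = 7.6, so 8 per group.
- d = 0.49: 5.23/0.240 = 21.8, so 22 per group.

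Power at 30 per group for d = 0.49 is 90.8%. The stated 8 to 22 per group and 91% reproduce. The calculation thus relies on three post-baseline visits, and two of them (months 6 and 9) fall where overlap is possible.

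**2. Who can qualify, counted from a dyad's own baseline.**

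| Window | Group 1 | Group 2 |
|---|---|---|
| Months 0–3 | No, in classes | No, waiting |
| Months 3–6 | Yes | No, in classes |
| Months 6–9 | Yes | Yes |

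Remaining follow-up at the earliest entry is 9 − 3 = 6 months in Group 1 and 9 − 6 = 3 months in Group 2. If the 6-month schedule in 11.1 governs, the months 3–6 window, open only to Group 1, is the whole remaining follow-up.

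**3. How many dyads.** Section 16.1 item 10 gives 5 + 5 = 10 dyads; 10/60 = 17%. With two interviews each, that is 20 interviews. If the 10 interviews in 12.3 are the full count, they cover 10/2 = 5 dyads; 5/60 = 8%.

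**4. Illustrative size.** The documents give no effect for the new material, so 0.1 to 0.3 SD is an assumption. The shift in a group contrast is (exposed in Group 1 − exposed in Group 2)/30 × effect.
- Month 3: nobody is eligible, so the shift is 0.
- Month 6, 5 Group 1 dyads exposed: 5/30 × 0.1 = 0.02 to 5/30 × 0.3 = 0.05 SD.
- Month 6, outer bound with all 10 dyads in Group 1 and exposed in time: 10/30 × 0.1 = 0.03 to 10/30 × 0.3 = 0.10 SD.
- Month 9, if the effect persists equally in both arms: a 5/5 split gives (5 − 5)/30 = 0; a 7/3 split gives 4/30 × 0.1 = 0.013 to 4/30 × 0.3 = 0.04 SD; a 3/7 split gives the same with the sign reversed.

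**The case against.** **Overlap may never happen.** Contact follows enrolment order, no start date is given, and 13.1 shows that the sub-study was planned after dyads had already reported trouble practising at home. The first dyads approached may be past month 9. This stands, and it rules out saying that the sub-study gives support to dyads in follow-up. The wording about current participants points the other way but does not settle it, and nothing in the rule prevents overlap.

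**Exposure before month 6 needs several steps in time.** First-wave material comes only after an interview and a development step, and the second wave comes after a further month of use and revision. By then Group 2 dyads from the earliest block of 10 may have finished too. This also stands: the case with all 10 dyads in Group 1 is a bound, not an expectation.

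**Everyone already gets support.** Section 16.1 item 9 gives all dyads a booklet and videos, and items 6 and 7 allow caregiver interviews and monthly calls about barriers to practice. The added support is therefore incremental. But 13.1 says the video already supplied seemed ineffective, and the new material is meant to do better.

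**Co-interventions are covered.** Item 7 of 16.1 records them monthly and 12.3 plans covariates for them. The sub-study is not named there. Joining it is a choice made after randomisation, so covariate adjustment is not a dependable repair.

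**Conclusion.** The entry rule leaves an avoidable route by which up to 10 of 60 dyads, or 5 if 12.3 is right, could receive extra home-practice support before their last outcome visit. Before month 6 that route is open only to Group 1. The likely effect is modest: about 0.02 to 0.05 SD at month 6 under the assumed 0.1 to 0.3 SD and 5 exposed Group 1 dyads, against pilot effects of 0.49 to 0.83. The month-3 contrast, the only one with a control group that has not yet started the programme, is untouched.

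A reader might infer three stronger conclusions, and the documents support none of them:
- **That contamination is built in.** The text shows only that it can happen.
- **That Group 1 is favoured for longer and at both later visits.** Each sub-study dyad has the same planned month of home use, and the direction at month 9 depends on an unknown mix of arms.
- **That the bias could be large.** Reaching 0.17 SD takes 10/30 × 0.5: all 10 dyads in Group 1, exposed in time, and an effect about equal to the 0.49 that the full class programme had on caregiver burden in the pilot.

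**What to change.** 1. In 16.1 item 10 and 20.1, make entry conditional on both members of the dyad having completed their last scheduled outcome assessment. Keep contact in enrolment order.
2. Withhold the new brochures and clips, including open posting on YouTube, from dyads still in follow-up.
3. Reconcile 11.1 (outcomes to month 6) with 12.3, 16.1 item 5 and 16.6 (month 9), so that the last visit is unambiguous. Reconcile the 10 interviews in 12.3 with the 10 dyads interviewed twice in 16.1.
4. If any dyad has already entered early, record the date and arm. Keep the intent-to-treat analysis as planned, and add a sensitivity analysis that leaves out that dyad's visits after entry.

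The cost is a wording amendment, a later sub-study start and slightly older recall of barriers. The trial's sample size and power do not change, and possible exposure falls from at most 10 dyads to none.
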